9.5.3 Appropriateness of Measurements

All clinical assessments are standard measurements commonly used in studies of obesity.

The safety assessments to be performed in this study, including hematology analyses, blood chemistry tests, urinalysis, and assessment of AEs, are standard evaluations to ensure subject safety.

9.5.4 Reporting of Serious Adverse Events, Pregnancy, and Events Associated with Special Situations

9.5.4.1 Reporting of Serious Adverse Events

All SAEs, regardless of their relationship to study treatment, must be reported on a completed SAE form by email or fax as soon as possible but no later than 1 business day from the date the investigator becomes aware of the event.

SAEs, regardless of causality assessment, must be collected through the through the last visit and for 28 days after the subject's last dose. All SAEs must be followed to resolution or, if resolution is unlikely, to stabilization. Any SAE judged by the investigator to be related to the study treatment or any protocol-required procedure should be reported to the sponsor regardless of the length of time that has passed since study completion.

The detailed contact information for reporting of SAEs is provided in the Investigator Study File.

For urgent safety issues, please ensure all appropriate medical care is administered to the subject and contact the appropriate study team member listed in the Investigator Study File.

It is very important that the SAE report form be filled out as completely as possible at the time of the initial report. This includes the investigator's assessment of causality.

Any follow-up information received on SAEs should be forwarded within 1 business day of its receipt. If the follow-up information changes the investigator's assessment of causality, this should also be noted on the follow-up SAE form.

Preliminary SAE reports should be followed as soon as possible by detailed descriptions including copies of hospital case reports, autopsy reports, and other documents requested by the sponsor.

The investigator must notify his/her IRB/IEC of the occurrence of the SAE, in writing, if required by their institution. A copy of this communication must be forwarded to the sponsor to be filed in the sponsor's Trial Master File.

9.5.4.2 Reporting of Pregnancy and Exposure to Study Drug through Breastfeeding

Any pregnancy in which the estimated date of conception is either before the last visit or within 28 days of last study treatment or any exposure to study drug through breastfeeding during study treatment or within 28 days of last study treatment must be reported.

If an adverse outcome of a pregnancy is suspected to be related to study drug exposure, this should be reported regardless of the length of time that has passed since the exposure to study treatment.

A congenital anomaly, death during perinatal period, an induced abortion, or a spontaneous abortion are considered to be an SAE and should be reported in the same time frame and in the same format as all other SAEs (see [Section 9.5.4.1](#)).

Pregnancies or exposure to study drug through breastfeeding must be reported by fax or email as soon as possible but no later than 1 business day from the date the investigator becomes aware of the pregnancy. The contact information for the reporting of pregnancies and exposure to study drug through breastfeeding is provided in the Investigator Study File. The Pregnancy Report Form must be used for reporting. All pregnancies must be followed to outcome. The outcome of the pregnancy must be reported as soon as possible but no later than 1 business day from the date the investigator becomes aware of the outcome.

A subject who becomes pregnant must be withdrawn from the study.

9.5.4.3 Reporting of Events Association with Special Situations

9.5.4.3.1 REPORTING OF ADVERSE EVENTS ASSOCIATED WITH STUDY DRUG OVERDOSE, MISUSE, ABUSE, OR MEDICATION ERROR

Adverse events associated with study drug overdose, misuse, abuse, and medication error refer to AEs associated with uses of the study drug outside of that specified by the protocol. Overdose, misuse, abuse, and medication error are defined as follows:

Overdose	Accidental or intentional use of the study drug in an amount higher than the protocol-defined dose
Misuse	Intentional and inappropriate use of study drug not in accordance with the protocol or authorized dose, route of administration, or indication(s) or use of prescription-only study drug without a prescription
Abuse	Sporadic or persistent intentional excessive use of study drug accompanied by harmful physical or psychological effects
Medication error	Any unintentional event that causes or leads to inappropriate study drug use or subject harm while the study drug is in the control of the healthcare professional, subject, or consumer. Such events may be related to professional practice, healthcare products, occupational exposure, procedures, or systems, including prescribing, order communication, product labeling, packaging, nomenclature, compounding, dispensing, distribution, administration, education, monitoring, or use.

All AEs associated with overdose, misuse, abuse, or medication error should be captured on the Adverse Event CRF and also reported using the procedures detailed in [Section 9.5.4.1](#) even if the AEs do not meet serious criteria. Abuse is always to be captured as an AE. If the AE associated with an overdose, misuse, abuse, or medication error does not meet serious

criteria, it must still be reported using the SAE form and in an expedited manner but should be noted as nonserious on the SAE form and the Adverse Event CRF.

9.5.4.3.2 REPORTING OF STUDY-SPECIFIC EVENTS

Study-specific events (listed below) should always be considered as serious important medical events and be entered on the Adverse Event CRF and reported using the procedures detailed in Reporting of Serious Adverse Events ([Section 9.5.4.1](#)), even if the study-specific event does not meet other serious criteria.

- Serotonin syndrome Must have at least 1 of the following: spontaneous clonus; inducible clonus plus agitation or diaphoresis; Ocular clonus plus agitation or diaphoresis; Tremor plus hyperreflexia; Hypertonia plus temperature above 38°C plus ocular clonus or inducible clonus
- Psychosis
- Suicidal behavior
- Priapism
- New onset of valvular heart disease
- New onset pulmonary hypertension
- Malignant neoplasms, with the exception of basal cell and squamous cell carcinomas of the skin
- Fibroadenomas of the breast or ductal carcinoma in situ

The following additional study specific AE of interest should be reported using the procedures detailed in Reporting of SAEs ([Section 9.5.4.1](#)), even if the study-specific event does not meet serious criteria. If the event meets seriousness criteria, it should be reported as an SAE as above. However, if the event listed below does not meet serious criteria, it should be noted as nonserious on the Adverse Event CRF:

- Suicidal ideation
- Euphoria

9.5.4.4 Expedited Reporting

The sponsor must inform investigators and regulatory authorities of reportable events, in compliance with applicable regulatory requirements, on an expedited basis (ie, within specific time frames). For this reason, it is imperative that sites provide complete SAE information in the manner described above.

9.5.4.5 Breaking the Blind

In the case of a medical emergency where the appropriate treatment of the subject requires knowledge of the study treatment given, the investigator may break the randomization code for an individual subject. In all such cases, the AE necessitating the emergency blind break will be handled as an SAE in accordance with the procedures indicated above. Any broken

code will be clearly justified and documented. The medical monitor must be notified immediately of the blind break.

9.5.4.6 Regulatory Reporting of Adverse Events

Adverse events will be reported by the sponsor or a third party acting on behalf of the sponsor to regulatory authorities in compliance with local and regional law and established guidance. The format of these reports will be dictated by the local and regional requirements.

9.5.5 Completion/Discontinuation of Subjects

The investigator may withdraw the subject from the study at any time for safety or administrative reasons. A subject may elect to discontinue the study at any time for any reason. All subjects will continue in the study until the 52-week evaluation is completed. Subjects who discontinue treatment prematurely will be followed up until study completion. All subjects who discontinue the study are to complete the study's early discontinuation procedures indicated in the Schedule of Procedures/Assessments [Table 2](#)).

The investigator will promptly explain to the subject involved that the study will be discontinued for that subject and provide appropriate medical treatment and other necessary measures for the subject. A subject who has ceased to return for visits will be followed up by mail, phone, or other means to gather information such as the reason for failure to return, the status of treatment compliance, the presence or absence of AEs, and clinical courses of signs and symptoms.

Subjects who discontinue early from the study will be discontinued for 1 of these primary reasons: AE(s), lost to follow-up, subject choice, withdrawal of consent, pregnancy, study terminated by sponsor, or other. In addition to the primary reason, the subject may indicate 1 or more of secondary reasons for discontinuation. Study disposition information will be collected on the Subject Disposition CRF.

Detailed retention strategies will be developed and included in study manual. These include a highly trained and competent staff, easy access to the clinic, reminder and follow-up calls, interactive group sessions with games and hands-on nutrition and physical activity demonstrations, random raffle drawings, social events, birthday and holiday cards, and newsletters. In addition, home visits for assessments of families will be an option, as needed, to maximize data collection. This detailed retention plan will help prevent missing data.

A subject removed from the study for any reason may not be replaced.

9.5.6 Abuse or Diversion of Study Drug

During the study, the investigator will report any concern about abuse or diversion of study drugs by completing the Abuse or Diversion of Study Drug CRF. The DEA Registrant has the responsibility to comply with local, state, and Federal laws to notify the Field Division Office of the DEA of any theft or significant loss of any controlled substances upon discovery of such theft or loss.

9.5.7 Confirmation of Medical Care by Another Physician

The investigator will instruct subjects to inform site personnel when they are planning to receive medical care by another physician. At each visit, the investigator will ask the subject whether he or she has received medical care by another physician since the last visit or is planning to do so in the future. When the subject is going to receive medical care by another physician, the investigator, with the consent of the subject, will inform the other physician that the subject is participating in the clinical study.

9.6 Data Quality Assurance

This study will be organized, performed, and reported in compliance with the protocol, SOPs, working practice documents, and applicable regulations and guidelines. Site audits will be made periodically by the sponsor's or the CRO's qualified compliance auditing team, which is an independent function from the study team responsible for conduct of the study.

9.6.1 Data Collection

Data required by the protocol will be collected on the CRFs and entered into a validated data management system that is compliant with all regulatory requirements. As defined by ICH guidelines, the CRF is a printed, optical, or electronic document designed to record all of the protocol-required information to be reported to the sponsor on each study subject.

Data collection on the CRF must follow the instructions described in the CRF Completion Guidelines. The investigator has ultimate responsibility for the collection and reporting of all clinical data entered on the CRF. The investigator or designee as identified on Form FDA 1572 must sign the completed CRF to attest to its accuracy, authenticity, and completeness.

Completed, original CRFs are the sole property of Eisai and should not be made available in any form to third parties without written permission from Eisai, except for authorized representatives of Eisai or appropriate regulatory authorities.

9.6.2 Clinical Data Management

All software applications used in the collection of data will be properly validated following standard computer system validation that is compliant with all regulatory requirements. All data, both CRF and external data (eg, laboratory data), will be entered into a clinical system.

9.7 Statistical Methods

All statistical analyses will be performed by the sponsor or designee after the study is completed and the database is locked and released for unblinding. Statistical analyses will be performed using WinNonlin and SAS software or other validated statistical software as required. Details of the statistical analyses will be included in a separate statistical analysis plan (SAP).

9.7.1 Statistical and Analytical Plans

The statistical analyses of study data are described in this section. Further details of the analytical plan will be provided in the SAP, which will be finalized before database lock and treatment unblinding.

9.7.1.1 Study Endpoints

9.7.1.1.1 PRIMARY EFFICACY ENDPOINT

- Change in BMI from Baseline to Week 52

9.7.1.1.2 SECONDARY EFFICACY ENDPOINTS

KEY SECONDARY ENDPOINT

- Proportion (%) of subjects achieving at least a 5% BMI reduction at Week 52

OTHER SECONDARY ENDPOINT

- Proportion (%) of subjects achieving at least a 5% BMI reduction at Week 12
- Proportion (%) of subjects achieving at least a 10% BMI reduction at Week 52
- Percentage change in BMI from Baseline to Week 52
- Association between change and percentage change in BMI from Baseline to Week 52 with the outcome of achieving at least a 5% BMI reduction at Week 12 (revised per Amendment 02)
- Association between the proportion (%) of subjects achieving at least a 5% or 10% BMI reduction at Week 52 with the outcome of achieving at least a 5% BMI reduction at Week 12 (revised per Amendment 02)
- Change in waist circumference from Baseline to Week 52
- Change in HbA_{1c} from Baseline to Week 52
- Change in fasting glucose, fasting insulin, and HOMA-IR from Baseline to Week 52
- Change in BP (systolic and diastolic) and heart rate from Baseline to Week 52
- Change in fasting lipid profile (total cholesterol, LDL cholesterol, HDL cholesterol, triglycerides) from Baseline to Week 52
- Proportion (%) of subjects with prehypertension or primary hypertension at Week 52
- Proportion (%) of subjects with dyslipidemia at Week 52

9.7.1.2 Definitions of Analysis Sets

- The Safety Analysis Set is the group of subjects who received at least 1 dose of study drug and had at least 1 postdose safety assessment.
- The Full Analysis Set (FAS) is the group of all randomized subjects regardless of adherence to study drug.
- Per-Protocol Analysis Set (PP) is the group of all randomized subjects who are 80% or greater compliant with study medication, completed the study, have no major protocol deviations, have no violations of inclusion or exclusion criteria, and have BMI data at Baseline and Week 52. The determination of subjects to be excluded from this population based on the above criteria and list of major protocol violations will be included in the SAP and finalized before data base lock.
- The PD Analysis Set is the group of subjects who had sufficient PD data to derive at least 1 PD parameter.
- The PK Analysis Set is the group of all randomized subjects from whom at least 1 valid lorcaserin plasma concentration was obtained with associated documented dosing history.
- The population PK/PD set is the group of randomized subjects with PK information and who have at least 1 adequately documented measurement of BMI.

9.7.1.3 Subject Disposition

The number of subjects screened and the number (percentage) of subjects who failed screening and the reasons for screen failure will be summarized, based on data reported on the CRF.

For study completion, the number (percentage) of treated subjects who completed study treatment and who discontinued from study treatment will be summarized according to the primary reason for discontinuation and also according to secondary reason(s) for discontinuation, based on data reported on the CRF. The number (percentage) will be presented by treatment. The reasons for discontinuation from study treatment will be documented in the CRF and source documentation.

9.7.1.4 Demographic and Other Baseline Characteristics

Demographic and other baseline characteristics for the FAS and Safety Analysis Sets will be summarized for each treatment group using descriptive statistics or frequency count. Continuous demographic and baseline variables include age, height, BMI, waist circumference, and weight; categorical variables include sex and race.

9.7.1.5 Prior and Concomitant Therapy

All investigator terms for medications recorded in the CRF will be coded to an 11-digit character code using the World Health Organization Drug Dictionary. The number (percentage) of subjects who took prior and concomitant medications will be summarized for the Safety Analysis Set by treatment group, Anatomical Therapeutic Chemical class, and World Health Organization Drug Dictionary preferred term (PT). Prior medications will be defined as medications that stopped before the first dose of study drug. Concomitant medications will be defined as medications that started on or after the date of the dosing of study drug and continued up to 30 days afterward.

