 8. Known secondary causes (genetic, endocrine, or metabolic) for obesity (eg, Prader-Willi syndrome, Bardet Biedl syndrome, Down’s Syndrome, untreated hypothyroidism, Cushing’s syndrome, daily systemic corticosteroid exposure for longer than 30 days, history of significant exposure to corticosteroids for chronic illness during the past year)
 9. Use of other products intended for weight loss including prescription drugs, over-the-counter (OTC) drugs, and herbal preparations within 1 month before Screening
 10. Use of any of the following medications:
 - a) Serotonergic drugs within 7 days (or 5 half-lives, whichever is longer) or monoamine oxidase inhibitors (MAOIs) within 30 days before Randomization, including:
 - selective serotonin reuptake inhibitors (SSRIs)
 - serotonin norepinephrine reuptake inhibitors (SNRIs)
 - tricyclic antidepressants (TCAs)
 - bupropion

- triptans
 - St. John's Wort
 - tryptophan
 - linezolid
 - dextromethorphan in any form (eg, OTC cold medicines)
 - lithium
 - tramadol
 - antipsychotics or other dopamine antagonists
- b) Others
- antiseizure medications including valproic acid, zonisamide, topiramate and lamotrigine
 - oral steroids (topical and inhaled steroids are acceptable)
 - stimulant medications (Ritalin, Concerta, Biphedamine and Dexedrine)
 - benzodiazepines
11. Use of drugs known to increase the risk for cardiac valvulopathy within 6 months before Screening, including but not limited to pergolide, ergotamine, methysergide, and cabergoline
 12. History or evidence of clinically significant disease (eg, malignancy; cardiac, respiratory, gastrointestinal, renal, or psychiatric disease) other than prediabetes (impaired fasting glucose or impaired glucose tolerance), Type 2 diabetes treated with oral anti-diabetic agents (excluding sulfonylurea) or non-insulin injectable antidiabetic agents, obstructive sleep apnea, dyslipidemia, and nonalcoholic fatty liver disease
 13. Use of Belviq XR within 6 months before Screening or hypersensitivity to Belviq XR or any of the excipients
 14. Significant change in diet or level of physical activity within 1 month before dosing or change in weight of more than 5 kg within 3 months before Screening
 15. Any use of a of very-low-calorie (<1000 calories/day) weight loss diet within 6 months before Screening
 16. History of alcohol or drug dependence or abuse
 17. Recreational drug use within 2 years before Screening
 18. Known to be human immunodeficiency virus positive

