 19. Known to have active viral hepatitis (B or C) (revised per Amendment 01)
 20. Malignancy within 5 years before Screening
 21. Unable to attend scheduled visits (eg, lack of transportation) or lack of a caregiver or guardian to supervise study participation
 22. Special needs subjects who are unable to comprehend study-related instructions (eg, mild to profound mental retardation [IQ <70], moderate to severe cognitive developmental delay, pervasive development disorders, autism)

23. Ongoing epilepsy or other seizure disorder, or use of medications for a seizure disorder within 6 months of screening or any time between screening and randomization
24. Subjects with a BP in the 95th percentile or greater for age, sex, and height on 2 separate readings recorded on 2 separate days. Those subjects who had uncontrolled hypertension at Screening can be rescreened more than 1 month after initiation or adjustment of antihypertensive therapy 1 time.
25. Currently enrolled in another clinical study or has used any investigational drug or device within 30 days before providing informed consent
26. Planned bariatric surgery during the study
27. Not suitable to participate in the study in the opinion of the investigator, including consideration of any existing physical, medical, or mental condition that prevents compliance with the protocol
28. Female subjects who are breastfeeding or pregnant at Screening or Baseline (as documented by a positive β -human chorionic gonadotropin test). A separate Baseline assessment is required if a negative screening pregnancy test was obtained more than 72 hours before the first dose of study drug.
29. Female subjects of childbearing potential who:
 - a. Had unprotected sexual intercourse within 30 days before study entry and who do not agree to use a highly effective method of contraception (eg, total abstinence, an intrauterine device, a double-barrier method [such as condom plus diaphragm with spermicide], a contraceptive implant, an oral contraceptive, or have a vasectomized partner with confirmed azoospermia) throughout the entire study period and for 28 days after study drug discontinuation
 - b. Are currently abstinent, and do not agree to use a double-barrier method (as described above) or refrain from sexual activity during the study period and for 28 days after study drug discontinuation

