9.4.6 Prior and Concomitant Therapy

Any medication (including OTC medications) or therapy administered to the subject during the study (starting at the date of informed consent) will be recorded on the Prior and Concomitant Medication Case Report Form (CRF) or Non-Pharmacological Procedures CRF. The investigator will record on the Adverse Event CRF any AE for which the concomitant medication/therapy was administered. If the concomitant medication/therapy is

being administered for a medical condition present at the time of entry into the study, the investigator will record the medical condition on the Medical History and Current Medical Condition CRF.

Other products intended for weight loss including prescription drugs, OTC drugs, and herbal preparations are prohibited as concomitant medications. OTC cold medicines containing dextromethorphan can be used for up to 7 days and study medication is temporarily stopped for that time period and resumed the next day after the OTC cold medicine is stopped. Any of the following serotonergic agents in combination with Belviq XR is prohibited:

a. Serotonergic drugs

- SSRIs
- SNRIs
- TCAs
- bupropion
- triptans
- St. John's Wort
- tryptophan
- MAOIs
- linezolid
- dextromethorphan
- lithium
- tramadol
- antipsychotics or other dopamine antagonists

b. Others

- antiseizure medications including valproic acid, zonisamide, and lamotrigine
- oral steroids (topical or inhaled steroids are acceptable)
- stimulant medications (Ritalin, Concerta, Biphedamine and Dexedrine)
- benzodiazepines

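### A medication started before first dose and still being taken is neither prior nor concomitant under Section 9.7.1.5, so it drops out of both by-arm tables

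*Protocol*

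**What the plan says.** Protocol Section 9.7.1.5 sets two date rules.

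- Prior: "Prior medications will be defined as medications that stopped before the first dose of study drug".
- Concomitant: "Concomitant medications will be defined as medications that started on or after the date of the dosing of study drug", with a further clause that sets a limit of 30 days afterward.

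Only these two categories are tabulated: "The number (percentage) of subjects who took prior and concomitant medications will be summarized for the Safety Analysis Set by treatment group". No separate category is defined for therapy ongoing at baseline.

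Section 9.4.6 governs collection and is wider. It covers "Any medication (including OTC medications) or therapy administered to the subject during the study (starting at the date of informed consent"). It then gives an instruction for the case where a concomitant therapy is being given for a condition the subject already had on entering the study: that condition goes on the medical history form. Section 9.4.6 therefore counts such therapy as concomitant.

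Section 9.3.2 accepts subjects who arrive on treatment. Criterion 12 exempts "Type 2 diabetes treated with oral anti-diabetic agents (excluding sulfonylurea) or non-insulin injectable antidiabetic agents". Criterion 24 allows a subject with uncontrolled hypertension to be "rescreened more than 1 month after initiation or adjustment of antihypertensive therapy". Criterion 29c turns on hormonal contraception that has been stable for at least 4 weeks before dosing and is kept unchanged during the study. Criterion 10b accepts topical and inhaled steroids.

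**The concern.** One definition is written on the stop date and the other on the start date, and together they do not cover every record. What falls between them is the usual form of background therapy: begun before randomization and carried through treatment.

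The by-arm medication tables are where a reader would look to see whether background antidiabetic or antihypertensive use was similar in the two groups. Section 9.7.1.1.2 lists HbA1c, fasting glucose, insulin, HOMA-IR, blood pressure and the proportion with prehypertension or primary hypertension as secondary endpoints, so the question will arise. The baseline variables named in Section 9.7.1.4 (age, height, BMI, waist circumference, weight, sex and race) do not include background therapy and so do not fill the gap. A table built to the letter would show no use of these drugs except where a record happened to start on study, and a reader could take that for absence of use.

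**Working it through.** The protocol states no figure to reproduce here. The check applies the two date rules to six start and stop patterns.

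**Inputs.** Section 9.7.1.5 gives the two definitions and the 30-day limit. For illustration, first dose is day 0 and last dose is day 364 (52 weeks × 7 days). The start and stop days are examples chosen to represent each pattern.

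**Rules as written.**
- Prior if stop < 0.
- Concomitant, limit counted from last dose: 0 ≤ start ≤ 364 + 30 = 394.
- Concomitant, limit counted from first dose: 0 ≤ start ≤ 30.

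| Pattern | Start, stop (day) | Prior | Concomitant, last dose + 30 | Concomitant, first dose + 30 |
|---|---|---|---|---|
| Stopped before first dose | −60, −5 | yes | no | no |
| Started before, stopped during treatment | −60, 100 | no | no | no |
| Started before, still ongoing | −60, 400 | no | no | no |
| Started on the day of first dose | 0, 20 | no | yes | yes |
| Started during treatment, ongoing | 50, 400 | no | yes | no |
| Started after the limit | 400, 410 | no | no | no |

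**First result.** Rows 2 and 3 are unclassified under both readings of the limit. The clause about continuing does not rescue them, because it is joined by *and* to the start-date condition.

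**Second result.** Row 5 changes with the anchor. Counted from first dose, a drug begun on day 50 is lost as well; counted from last dose, it is kept. The sentence refers to the date of dosing without saying which dose.

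**Match to the admitted population.** Antihypertensive therapy initiated to allow rescreening must begin before rescreening, hence before day 0, and if continued it falls in row 2 or 3. A hormonal contraceptive stable for at least 4 weeks before dosing has a start date before day 0 and is meant to continue. A permitted antidiabetic already in use at entry has the same pattern.

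**After the fix.** Concomitant becomes (start < 0 and stop ≥ 0) or (0 ≤ start ≤ 394). Rows 2 and 3 become concomitant, rows 4 and 5 are concomitant, row 1 stays prior and row 6 stays outside. Every record starting by day 394 then falls in exactly one category.

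**The case against.** The strongest reply is that this is a drafting slip with little consequence. Section 9.4.6 shows the intended meaning, Section 9.7.1 leaves further detail to a SAP finalized before database lock, and no efficacy analysis in Section 9.7.1.6 uses the medication table. Most of that stands, and it limits the consequence. It does not remove the fault: Section 9.7.1.5 fixes the definition rather than deferring it, so a SAP that followed it would repeat the gap and one that corrected it would depart from the protocol. The conflict with Section 9.4.6 is itself something to settle.

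Four stronger readings are tempting, and the documents do not support them.

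- *Reviewers of individual adverse events or interactions would lack these drugs.* Section 9.4.6 records all medication from consent, and Table 2 schedules a medication assessment at every visit, including unscheduled and early-discontinuation visits. The record exists; only the summary misses it.
- *All background medication is lost.* That restates the rule and is not a size. A dose or product change entered as a new record with an on-study start date would be counted. Inclusion criterion 1 asks for healthy adolescents, and the protocol gives no figure for how many would be on a permitted background drug.
- *The 30-day window is wrong because treatment-emergent events use 28 days.* Nothing requires the two to match. Counted from last dose, 30 days covers the 28-day period.
- *The endpoint results are biased.* The table is descriptive and enters no planned efficacy model.

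**Conclusion.** The definition is wrong as written. Any medication record that starts before first dose and is still running at first dose is excluded from both summaries, whichever way the 30-day limit is read, and this contradicts how Section 9.4.6 uses the term. The unclear anchor of that limit is a second, separate defect in the same sentence.

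The effect is confined to the descriptive by-arm medication tables. Collection, review of individual events, the primary analysis, power and alpha are unaffected. The number of subjects concerned cannot be stated from the protocol. The conclusion assumes that the tables are programmed to the literal wording; the SAP is not shown and may already put this right. It is worth correcting because the therapies omitted are ones the eligibility criteria knowingly allow and ones a reader of the glycemic and blood pressure endpoints would want to see by arm.

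**What to change.** Replace the concomitant definition in Section 9.7.1.5 with: any medication that (a) started before first dose of study drug and was ongoing at first dose, or (b) started on or after first dose and up to 30 days after last dose. This keeps the stated 30 days and anchors it to last dose. Leave the prior definition as it is, and carry the same wording into the SAP so that it agrees with Section 9.4.6.

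The cost is one sentence and the matching line in the table programming. No new data are needed, since medication is already recorded from consent onward.
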